4.5 Analysis of the primary endpoint

The change from baseline in DAS28-CRP at week 12 will be analyzed using the method described in Section 2.4.1.

The primary analysis will be performed on the Per-protocol set (W12 PPS) which is the most conservative approach to show equivalent efficacy as this analysis set is the “cleanest” sample of the study population to identify differences, if there are any.

The MMRM will include the patient into the analysis as long as there is at least one non-missing DAS28-CRP change from baseline value.

The stratification factors in the primary analysis model will use the data from clinical database as it is most correct data and there are known incorrect stratification assignments in IRT data.

Table 4-1 MMRM Analysis SAS® Code

```
/* Save the LS Means and the differences into datasets */
ods output Diff = Diff LSMeans = LSMeans;
proc mixed data=DATASETNAME method=reml covtest;
  class VISIT TREATMENT USUBJID REGION RA_MED BODY_WEIGHT;
  model CHG = BSL VISIT TREATMENT VISIT*TREATMENT REGION
    RA_MED BODY_WEIGHT / solution ddfm=KR;
  repeated VISIT / type=un subject=USUBJID;
  lsmeans TREATMENT / diff CL;           /* Overall treatment effect */
  lsmeans VISIT*TREATMENT / diff CL;   /* treatment effect per visit */
run;
```

Note: names in capitals are only placeholders for the real dataset or variable names; select the model parameter estimations at visit Week 12 only from the SAS output datasets.

Sensitivity analysis of primary endpoint:

- Repeat the primary analysis based on SP1 FAS
- Repeat the primary analysis using IRT stratification data
- Repeat the primary analysis using the statistical model with treatment as fixed effect and body weight as continuous covariate (i.e., other stratifications like region and prior therapy will be excluded from the model)
- Repeat the primary analysis using the statistical model with treatment as fixed effect only

- Repeat the primary analysis by ADA status up to Week 12 (Positive/Negative)

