#### **6.4.1 Assessment of Disease Activity Score (DAS28)**

The disease activity score (DAS) is a combined index to measure the disease activity in patients with RA. In this study DAS28-CRP and DAS28-ESR will be measured. The DAS28-CRP will be used for primary and key secondary endpoint analysis, whereas DAS28-ESR will only be used for secondary endpoint analysis. The efficacy assessments will be done at screening, baseline, Week 2, Week 4, Week 12, Week 24 and Week 48 (Visits 1, 2, 3, 4, 8, 14 and 16).

In order to calculate the DAS28-CRP or DAS28-ESR, information about the following disease variables is needed:

The number of swollen joints and tender joints should be assessed using 28-joint count (TJC28 and SJC28), see [Figure 6-1](#).

The patient's general health (GH) or global disease activity measured on a Visual Analogue Scale (VAS) of 100 mm (both are useable for this purpose) must be obtained ([Prevoo et al 1995](#)).

CRP should be measured in mg/L

and

ESR should be measured in mm/hour.

Using this data, the DAS28 can be calculated using the following formula:

**DAS28-CRP** = 0.56 \* sqrt(TJC28) + 0.28\* sqrt(SJC28) + 0.36 \* ln(CRP+1) + 0.014 \* GH + 0.96

**DAS28-ESR** = 0.56 \* sqrt(TJC28) + 0.28 \* sqrt(SJC28) + 0.70 \* ln(ESR) + 0.014 \* GH

Swollen joints, tender joints and patient's general health assessment will be entered into the eCRF and CRP/ESR will be used to determine DAS28-CRP and DAS28-ESR scores.

In addition CRP values provided by the central laboratory at both screening and Week 22 will be entered into the eCRF and be used to calculate DAS28-CRP scores for the purpose of assessing eligibility at randomization and Week 24 only (see [Table 6-1](#)).

The DAS28 provides a number on a scale from 0 to 10 indicating the current activity of the RA of the patient. Disease activity definition is described in [Table 6-2](#).

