### **9.4.2 Statistical hypothesis, model, and method of analysis**

The following statistical hypotheses will be used to assess equivalence between GP2017 and US-licensed Humira® with regards to DAS28-CRP change from baseline at Week 12:

$$H_0: |GP2017 - \text{Humira}^{\circledR}| \geq 0.6 \quad \text{versus} \quad H_1: |GP2017 - \text{Humira}^{\circledR}| < 0.6$$

To address both EMA and FDA regulatory requirements for establishing therapeutic equivalence both 95% and 90% confidence intervals shall be estimated and used to assess equivalence of DAS28-CRP change from baseline at Week 12.

Therapeutic equivalence in terms of DAS28-CRP will be concluded if the 95% (as required by EMA) or 90% (as required by FDA) confidence interval for the difference in DAS28-CRP change from baseline at Week 12 between the two treatment groups is completely contained within the interval [-0.6; 0.6]. This is statistically equivalent to calculating two independent one-sided tests at a 2.5%/5% alpha level (one in each direction), of which both have to be successful.

A mixed-model repeated measures (MMRM) analysis will be performed for DAS28-CRP change from baseline as the endpoint including treatment, stratification factors, time, the interaction between time (visits) and treatment all as categorical variables, and baseline DAS28-CRP as a continuous variable.

$$DAS28CRP_{CFB} = \text{treat} + \text{strata} + \text{time} + (\text{time} * \text{treat}) + \text{baseline DAS28CRP}$$

MMRM is a standard approach to longitudinal analysis of continuous endpoints. Its roots bear into linear mixed modeling methodology and it is specified as a multivariate normal model of the longitudinal data. More specifically, this model includes a saturated visit-by-treatment structure for the mean. That is, time is considered as a factor rather than a continuous variable, and thus MMRM makes no assumption about trends over time. Traditional linear mixed models make further assumptions about the covariance of within/intra-patient observations, which can either originate from random effects or residual errors. With MMRM the covariance structure is specified only through the residual error term. The most flexible covariance matrix is unstructured, that is, all variance and covariance parameters are estimated. The actual covariance matrix to be used shall be determined within the statistical analysis plan prior to unblinding.

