2.4.1 Analysis of the primary endpoint

The following statistical hypotheses will be used to assess equivalence between GP2017 and US-licensed Humira® with regards to DAS28-CRP change from baseline at Week 12:

$H_0: |GP2017 - \text{Humira}^\circledR| \geq 0.6$ versus $H_1: |GP2017 - \text{Humira}^\circledR| < 0.6$

To address both EMA and FDA regulatory requirements for establishing therapeutic equivalence both 95% and 90% confidence intervals will be estimated and used to assess equivalence of DAS28-CRP change from baseline at Week 12.

Therapeutic equivalence in terms of DAS28-CRP will be concluded if the 95% (as required by EMA) or 90% (as required by FDA) confidence interval for the difference in DAS28-CRP change from baseline at Week 12 between the two treatment groups is completely contained within the interval [-0.6, 0.6]. This is statistically equivalent to calculating two independent one-sided tests at 2.5%/5% alpha level (one in each direction), of which both have to be successful.

A mixed-model repeated measures (MMRM) analysis will be performed for DAS28-CRP change from baseline up to Week 12 as the endpoint, including treatment, stratification factors (region, body weight category, prior systemic therapy), time, the interaction between time (visits) and treatment all as categorical variables, and baseline DAS28-CRP as a continuous variable in the model.

DAS28CRP CFB = treat + strata + time + (time*treat) + baseline DAS28CRP

In the case that the IRT and eCRF values of the stratification factors differ the correct definition of the stratification factors used for the primary analyses will be based on the clinical database.

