2.5 Determination of sample size

2.5.1 Sample size calculation for the primary endpoint analysis

The sample size for this study is based on an expected difference of zero and common SD of 1.30 for the DAS28-CRP change from baseline at Week 12 (ReAct study), an equivalence margin of 0.6 and assumed loss of 20% patients from the per-protocol analysis set. A 0.6 change in DAS28-CRP score is considered as no clinically meaningful difference by EULAR criteria and is therefore used as the equivalence margin limits [-0.6; 0.6].

In order to fulfil FDA regulatory requirements for establishing therapeutic equivalence (e.g. using 90% confidence interval), a sample size of 154 patients per treatment group (to maintain overall 246 evaluable patients for the primary endpoint analysis) will have 95% power to test the equivalence between GP2017 and US-licensed Humira®.

In order to fulfil EMA regulatory requirements for establishing therapeutic equivalence (e.g. using 95% confidence interval), a sample size of 154 patients per treatment group (to maintain overall 246 evaluable patients for the primary endpoint analysis) will have 90% power to test the equivalence between GP2017 and US-licensed Humira®.

[figure not shown]

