2.5.2 Power for analysis of key secondary endpoint

From [Burmester et al \(2014\)](#) the standard deviation of the change from baseline of the DAS28-CRP at 6 months, i.e. roughly Week 24, was observed as 1.5. This is comparable with the value of 1.3 found by [Burmester et al \(2014\)](#) for the Week 12 assessment. This matches well with [Wells et al \(2009\)](#) who found that the standard deviation of the DAS28-CRP was 0.9 to 1.0, which would mean a change from baseline measurement could be expected to have an SD of 1.4 times of the baseline SD (provided the baseline and post-baseline measurements were independent).

The time weight average is a weighted score of four change values where the weights sum to 1. The exact value of the SD for the time-weight average is unknown because it depends on both the days of each visit for each subject and the correlation between the individual measurements. However, a range for the SD can be estimated. Assuming each DAS28-CRP change from baseline value has a common SD of 1.4 then the lowest possible SD for the time-weighted average will occur if all four changes scores are independent and equally spaced, so that the weights are all 0.25, and this is then the same as taking an average of four independent random variables, and in this case the standard deviation of the time-weighted value will be $\frac{1}{2}$ of common SD, i.e. 0.7. At the other extreme the maximum of the weighted average occurs if each change score is perfectly correlated with the others. Then the specific values of the weights are irrelevant as the weighted average, will be the same as a single value of the change score, and hence will have an SD of 1.4.

[Figure 2-2](#) below shows the resulting power for different values of the SD for the time-weighted average with 246 evaluable patients when calculating both 90% and 95% confidence interval. It is clear that there is always sufficient power (at least 80%) to demonstrate equivalence using the 90% confidence interval, and that the power will also be sufficient using the 95% confidence interval.

Figure 2-2 Power of AUEC analysis for various common standard deviations

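### The primary MMRM shares one baseline slope across Weeks 2, 4 and 12; a baseline-by-visit term costs almost nothing and may recover some Week 12 precision

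*SAP*

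**What the plan says.** The primary model is stated three times, each time with one baseline coefficient.

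- SAP 4.5, Table 4-1: "model CHG = BSL VISIT TREATMENT VISIT*TREATMENT REGION", followed by the other stratification factors.
- SAP 2.4.1: "DAS28CRP CFB = treat + strata + time + (time*treat) + baseline DAS28CRP".
- Protocol 9.4.2: "the interaction between time (visits) and treatment all as categorical variables, and baseline DAS28-CRP as a continuous variable". Only treatment is crossed with time.

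The response is "DAS28-CRP change from baseline up to Week 12 as the endpoint" (SAP 2.4.1). Under the protocol 6.4.1 schedule ("The efficacy assessments will be done at screening, baseline, Week 2, Week 4, Week 12, Week 24 and Week 48") the post-baseline visits in the model are therefore Weeks 2, 4 and 12. The covariance is unstructured: "repeated VISIT / type=un subject=USUBJID".

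None of the five sensitivity analyses in SAP 4.5 lets the baseline slope vary by visit, and no reason is given for holding it constant. SAP 4.6.1.2 reuses the same MMRM for DAS28-CRP and DAS28-ESR at all visits.

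**The concern.** In a regression of change on baseline, the slope is cov(baseline, visit score) / var(baseline) - 1. If a patient's score drifts away from its baseline value over time while the visit SDs stay similar, the covariance falls and the slope steepens from Week 2 to Week 12. A single slope is then a compromise. At Week 12 it under-adjusts, and part of the baseline variance stays in the residual.

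The equivalence decision depends on whether the Week 12 confidence interval fits inside [-0.6; 0.6], so avoidable width matters. It would matter most if the true difference were not zero or the SD exceeded the planning value. The model is otherwise built to be flexible over time, with visit as a factor and an unstructured covariance, so the restriction on baseline stands out.

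**Working it through.** **Step 1. Reproduce the planned power.** Inputs from SAP 2.5.1: "expected difference of zero and common SD of 1.30 for the DAS28-CRP change from baseline at Week 12", margin 0.6, 246 evaluable patients (123 per arm).

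- SE = 1.30 × sqrt(2/123) = 0.1658, and 0.6/0.1658 = 3.619.
- Power = 2Φ(0.6/SE - z) - 1.
- 95% CI (z = 1.960): 90.3%, against 90% stated. 90% CI (z = 1.645): 95.2%, against 95% stated.

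The planned figures reproduce. They use the SD of the raw change, with no credit for baseline adjustment.

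**Step 2. Can the documents fix the Week 12 slope?** SAP 2.5.2 gives a DAS28-CRP score SD of 0.9 to 1.0; take 0.95 as the baseline SD. Since var(change) = SDb² + SD12² - 2cov, cov = (SDb² + SD12² - 1.30²)/2. The Week 12 score SD (SD12) is not given, so it is varied:

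- SD12 = 0.95: cov = (0.9025 + 0.9025 - 1.69)/2 = 0.0575; slope = 0.064 - 1 = -0.94.
- SD12 = 1.2: cov = 0.326; slope = 0.361 - 1 = -0.64.
- SD12 = 1.3: cov = 0.451; slope = 0.50 - 1 = -0.50.

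The documents do not determine the Week 12 slope, and they give no slopes for Weeks 2 and 4.

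**Step 3. Size under assumed slopes.** With complete data and balanced arms, the ratio of Week 12 SEs (one slope / visit-specific slopes) is sqrt(1 + d² × SDb²/s12²). Here:

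- s12² = 1.30² - b12² × SDb² is the Week 12 residual variance. For b12 = -0.5, s12 = 1.210; for b12 = -0.94, s12 = 0.945.
- c = 1'Σ⁻¹b / 1'Σ⁻¹1 is the common slope under residual covariance Σ, and d = b12 - c.

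Assumed: residual correlation 0.6, and Week 2 and Week 4 residual SDs either equal to Week 12 or 0.7 and 0.85 times it.

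| Slopes W2/W4/W12 | Early residual SDs (× Week 12) | c | d | SE excess | 95%-CI power, free / one slope |
|---|---|---|---|---|---|
| -0.2/-0.3/-0.5 | 1, 1 | -0.333 | -0.167 | 0.9% | 94.6% / 94.2% |
| -0.2/-0.3/-0.5 | 0.7, 0.85 | -0.232 | -0.268 | 2.2% | 94.6% / 93.5% |
| -0.5/-0.7/-0.94 | 1, 1 | -0.713 | -0.227 | 2.6% | >99% / >99% |
| -0.5/-0.7/-0.94 | 0.7, 0.85 | -0.560 | -0.380 | 7.0% | >99% / >99% |
| -0.3/-0.5/-0.94 | 1, 1 | -0.580 | -0.360 | 6.4% | >99% / >99% |
| -0.3/-0.5/-0.94 | 0.7, 0.85 | -0.364 | -0.576 | 15.6% | >99% / 98% |
| equal | either | same | 0 | 0% | identical |

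Example, last unequal row: 0.576² × 0.9025/0.8926 = 0.3355, and sqrt(1.3355) = 1.156. The lowest 90%-CI power with one slope is 96.9% (second row), against 95% stated.

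**Step 4. Bias, error rate and cost.** A separate set of simulations (4,000 trials per scenario, 123 per arm, complete data) took assumed slopes from equal to a deliberately extreme -0.11/-0.25/-0.73. The SE ratio ran from 0.999 to 1.11. Neither model showed bias. With the 95% CI, false equivalence at a true difference of 0.6 was 2.0% to 2.8% for both models (nominal 2.5%). With equal slopes, the extra terms cost about 0.1% of the SE. With the Week 12 change SD scaled to 1.30 (baseline SD 0.9), the one-slope power for the 95% CI was 91.0% or more.

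**Step 5. Where power would slip.** In a grid over the slope gap |d| (0 to 0.4) and Week 12 slope (-0.3 to -0.7), with baseline SD 0.9 or 1.0, 95%-CI power fell below 90% (88.7-89.1%) only for a gap of 0.4 with a Week 12 slope of -0.3. The common slope would then be +0.1 or -0.7, that is, of opposite sign or more than twice as steep.

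**The case against.** A reader might infer that the SAP's own figures imply a Week 12 slope near -0.94, so that the shared slope certainly inflates the standard error and erodes power. The documents do not support this, for four reasons.

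- The -0.94 needs equal score SDs at baseline and Week 12, which is stated nowhere, and it joins a score SD and a change SD taken from different cited studies.
- The phrase "provided the baseline and post-baseline measurements were independent" in SAP 2.5.2 is a proviso in a rough plausibility check, not an assumption about this trial.
- The same section assumes a common SD of 1.4 for every change value. By the same equal-SD reasoning, that gives the same slope at each visit and no loss at all. It too is a simplification, but one half of the section cannot be used without the other.
- The large excesses arise where baseline already explains much of the Week 12 variance. Even at 15.6%, the one-slope residual SD is 0.945 × 1.156 = 1.09, well below the planned 1.30.

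A wider interval also makes equivalence harder to claim, so the restriction is conservative. All of this stands, and it settles the certainty and the severity. It does not supply a reason for the restriction, which saves about 0.1% of the SE at best.

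**Conclusion.** The shared slope is a fact of the plan. Its effect is conditional: nothing if the slopes are equal, and about 1% to 16% of the Week 12 SE across the three unequal-slope scenarios, with the upper end needing both a steep Week 12 slope and smaller early-visit residuals. The slopes, the correlation of 0.6, the early residual SDs and complete data are assumptions; the baseline SD of 0.95 is the midpoint of the SAP's range.

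The loss is one of precision only. With randomised arms and near-complete Week 12 data in the W12 PPS, there is no bias and no inflation of type I error. The planned power holds in all three scenarios. This is a minor point, and the change is a free improvement, not a correction of an error.

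**What to change.** - Add BSL*VISIT to the MODEL statement in SAP Table 4-1 and a baseline-by-time term to the formula in SAP 2.4.1.
- Use the same model for the SP1 FAS repeat and for the DAS28-CRP and DAS28-ESR MMRMs in SAP 4.6.1.2.
- Record it in SAP section 3 as a change from protocol 9.4.2, before database lock and unblinding, so that it is not an unlisted departure.

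The cost is one term in the code and two degrees of freedom with three visits (one fewer than the number of visits in the longer models). If the sponsor prefers to keep the protocol model as primary, the minimum is to pre-specify the version with BSL*VISIT as a further sensitivity analysis in SAP 4.5.

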4.6 Analysis of secondary endpoints

4.6.1 Efficacy evaluation

4.6.1.1 Key secondary endpoint: Time-weighted averaged change from baseline in DAS28-CRP until Week 24

The averaged change from baseline in DAS28-CRP between Week 2 and Week 24 (standardized AUEC approach), will be estimated by a weighted mean across visits. The weights are derived using the standard formula from the trapezoidal rule across the visits. Mean averaged change from baseline from Week 2 to Week 24, standard errors and the two-sided 95%/90% CI for the mean difference between GP2017 and Humira® will be estimated from the ANCOVA model and the 95%/90% CI compared to the pre-specified equivalence margin of [-0.6; 0.6].

The time-weighted averaged change from baseline is defined as the change from baseline of DAS28-CRP in Weeks 2, 4, 12 and 24, weighted based on the time intervals between the actual dates of two consecutive visits in days. The scheduled visits which are outside the allowed time window can be used for the calculation (e.g., the End of Study visit for early discontinued patients). Unscheduled visits or repeat measurements will not be used in the calculation of the time-weighted averaged change from baseline.

In general, the time-weighted averaged change from baseline will be derived using following formula:

$$\text{time weighted averaged CFB} = \frac{\sum_{i=1}^k 0.5 \times (c_i + c_{i-1}) \times (d_i - d_{i-1})}{\sum_{i=1}^k (d_i - d_{i-1})}$$

Where k = number of timepoints (will be 4 if all DAS28-CRP values up to Week 24 are present)

d_i = study day based on the actual visit dates (see Section 4.1.3)

c_i = change from baseline in DAS28-CRP on d_i , where c_0 refers to baseline and is defined as zero.

If c_m value (where $m < k$) is missing, c_m shall be set equal to c_{m-1} and $d_i = d_{i-1}$ for the calculation.

The time-weighted averaged change from baseline analysis will be performed using Analysis of Covariance (ANCOVA). The model will include following terms: treatment group, body-weight category, prior systemic therapy, and region as factors and baseline DAS28-CRP value as continuous covariate. In the case that the IRT and eCRF values of the stratification factors differ the correct definition of the stratification factors used for the analyses will be based on the clinical database.

Table 4-2 ANCOVA analysis SAS® Code

```
/* Save the LS Means and the differences into datasets */
ods output Diff = Diff LSMeans = LSMeans;
proc mixed data=DATASETNAME covtest;
  class TREATMENT REGION RA_MED BODY_WEIGHT;
  model time-weighted averaged CFB = BSL TREATMENT REGION RA_MED
    BODY_WEIGHT / s ddfm=KR;
  lsmeans TREATMENT / diff CL;
run;
```

Note: names in capitals are only placeholders for the real dataset or variable names

Sensitivity analysis of key secondary endpoint:

- Repeat the key secondary analysis based on SP1 FAS
- Repeat the key secondary analysis using IRT stratification data
- Repeat the key secondary analysis using the statistical model with treatment as fixed effect and body weight as continuous covariate (i.e., other stratifications like region and prior therapy will be excluded from the model)
- Repeat the key secondary analysis using the statistical model with treatment as fixed effect only
- Repeat the key secondary analysis by ADA status up to Week 24 (Positive/Negative)

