Data analysis	To conclude equivalence between GP2017 and US-licensed Humira® with regards to DAS28-CRP change from baseline at Week 12, both the 90% and 95% CI of the treatment difference must be completely contained within the interval [-0.6, 0.6]. Treatment estimates and 90/95%

	
CI shall be estimated using a mixed-model repeated measures (MMRM) model.
 
Time-weighted averaged change from baseline in DAS28-CRP until Week 24 (standardized AUEC approach) will be estimated using the same MMRM used to analyze the primary endpoint.

Key words	Similar efficacy, safety and immunogenicity GP2017 to US-licensed Humira® in patients with rheumatoid arthritis (RA).

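### The key secondary time-weighted average ends at a patient's last DAS28-CRP visit but is analysed as a 24-week value: a modest distortion, mainly in the SP1 FAS sensitivity analysis

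*SAP*

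**What the plan says.** SAP 4.6.1.1 defines each patient's value as the trapezoid sum of DAS28-CRP changes over k intervals, divided by the total days in those same intervals. The baseline change is set to zero, and k is the "number of timepoints (will be 4 if all DAS28-CRP values up to Week 24 are present". The rule for a missing value covers only points before the last one, so it closes gaps but does not carry follow-up forward. Those who stop early are kept in: "The scheduled visits which are outside the allowed time window can be used for the calculation (e.g., the End of Study visit for early discontinued". SAP 2.4.2 adds that the computed average is not imputed.

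The ANCOVA has terms for treatment, the three stratification factors and baseline DAS28-CRP. It has none for length of follow-up.

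The main key secondary analysis uses SP1 PPS, which by SAP 2.7.2 contains only patients who complete Week 24. The first listed sensitivity analysis is "Repeat the key secondary analysis based on SP1 FAS". The others change the source of the strata, the covariates or the ADA subgroup.

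The protocol describes the method in two ways. Its summary says the endpoint "will be estimated using the same MMRM used to analyze the primary endpoint", while section 9.5.1.1 specifies an ANCOVA, as the SAP does.

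**The concern.** Two features push a shortened average towards zero. The response normally builds over time, and the zero at baseline takes a larger share of a short window than of a long one. A patient with exactly the same course therefore scores a smaller improvement if follow-up stops sooner.

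In the FAS analysis, two products with identical effects would then appear different if one arm lost more patients early. For an equivalence trial the opposite direction matters more. Shortened windows compress a true difference even when withdrawal is equal, and can hide more of it if the comparator loses more patients early. The FAS repeat is the only listed form of the key secondary analysis that contains withdrawn patients, so it is where a reader would look to see whether the completer result is robust.

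**Working it through.** **The plan's own figures.** Inputs from SAP 2.5.1: "The sample size for this study is based on an expected difference of zero", "common SD of 1.30 for the DAS28-CRP change from baseline at Week 12" and "an equivalence margin of 0.6 and assumed loss of 20% patients from the per-protocol analysis set". SAP 2.4.1 uses "two independent one-sided tests at 2.5%/5% alpha level (one in each direction"). With 246 evaluable patients, n = 123 per arm.
- SE = 1.30 × √(2/123) = 0.166, and 0.6/SE = 3.62.
- Power = 2Φ(3.62 − z) − 1, which is 95.2% for the 90% CI (z = 1.645) and 90.3% for the 95% CI (z = 1.960).
- 123/0.8 = 153.75, so 154 per arm.

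The stated 95%, 90% and 154 are reproduced.

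**Weights implied by SAP 4.6.1.1 at nominal weeks.**
- To Week 24: half the adjacent spans are (4−0)/2 = 2, (12−2)/2 = 5, (24−4)/2 = 10 and (24−12)/2 = 6. The weights are 2/24, 5/24, 10/24 and 6/24, sum 0.958.
- To Week 12: 0.167, 0.417 and 0.333, sum 0.917.
- To Week 4: 0.50 and 0.25, sum 0.75.

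**Effect of stopping.** The documents give no DAS28-CRP course, so four are assumed for Weeks 2, 4, 12 and 24. Week 16 and 20 stops assume an attended End of Study visit, with its value interpolated linearly between Weeks 12 and 24. Gaps to the 24-week value are in brackets.

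| Assumed course | To Week 24 | Stop Week 4 | Stop Week 12 | Stop Week 16 | Stop Week 20 |
|---|---|---|---|---|---|
| Flat: −2.0 throughout | −1.92 | −1.50 (0.42) | −1.83 (0.08) | −1.88 (0.04) | −1.90 (0.02) |
| Slow: −0.5, −0.9, −1.8, −2.2 | −1.53 | −0.48 (1.05) | −1.06 (0.47) | −1.26 (0.27) | −1.41 (0.12) |
| Middle: −0.9, −1.3, −2.0, −2.3 | −1.75 | −0.78 (0.98) | −1.36 (0.40) | −1.53 (0.22) | −1.66 (0.10) |
| Fast: −1.2, −1.7, −2.1, −2.2 | −1.88 | −1.03 (0.85) | −1.61 (0.27) | −1.74 (0.14) | −1.82 (0.06) |

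**Spurious difference with no true difference** = excess withdrawal fraction × gap. For 10 points:
- Week 4 stops: 0.04 to 0.11.
- Week 12 stops: 0.01 to 0.05.
- Week 16 and 20 stops: 0.022 and 0.010 on the middle course; 0.002 to 0.027 over all four.

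Reaching 0.6 through Week 4 stops alone would need 0.6/1.05 to 0.6/0.85, an imbalance of about 57 to 70 points on the improving courses.

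**Simulation.** Assumptions: 154 per arm, 4,000 runs, SD 1.3, within-patient correlation 0.6, middle course, withdrawal unrelated to outcome, no covariates. The implied SD of the 24-week average is 1.06, inside the plan's range of 0.7 to 1.4.
- No true difference, 20% against 10% stopping: shift 0.095 at Week 4 and 0.040 at Week 12. The 95% CI lies within the margin in 97.8% and 99.4% of runs, against about 99.6% with equal withdrawal. With 30% against 10% at Week 4, the shift is 0.19 and the chance 90.1%.
- True 24-week difference of 0.6, GP2017 worse and growing in proportion to response, where false equivalence should be about 2.5%. With 20% stopping at Week 4 in both arms, the mean estimate is 0.53 and false equivalence 8.6%. With 10% GP2017 against 20% Humira, they are 0.47 and 17.8%. The same two patterns at Week 12 give 3.9% and 5.9%.
- If the true difference is constant over visits, the two Week 4 figures fall to about 4% and 14-15%.
- A likelihood estimate of the fixed 24-week average from all observed visits gave a spurious difference of −0.002 to 0.003 and false equivalence of about 2-3%.

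**The case against.** The other side has real force on scale and placement.

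- **No stated decision rests on the affected analysis.** A reader might infer that the equivalence claim itself is compromised. The documents do not support that. The key secondary conclusion is drawn on SP1 PPS, and neither document sets a success rule for the FAS repeat. The PPS is touched only where a Week 24 completer lacks a Week 24 component such as CRP, so that the average ends at Week 12.
- **The window is often longer than 4 or 12 weeks.** A reader might assume that every stopper is cut back to the last scheduled visit. Protocol section 6 asks early stoppers to attend as soon as possible for the Visit 16 assessments, and SAP 4.6.1.1 uses that visit at its actual date. The Week 4 and Week 12 figures apply to stops at about those times, or to patients who decline the visit.
- **The larger simulated figures use heavy early loss.** Protocol section 4 anticipates 20% dropout after randomization, not split by arm or time. Twenty percent of an arm stopping by Week 4 is a stress case.
- **Part of the remedy is already planned.** SAP 4.6.1.2 fits the MMRM at all visits, and SP1 data are analysed on the FAS as well as the PPS. FAS differences by visit, free of this truncation, will be available.
- **The protocol does not clearly require an MMRM here.** Its summary says so, but section 9.5.1.1 says ANCOVA. This is an unreconciled inconsistency, not evidence that the SAP abandoned the protocol's method.
- **The MMRM answers a somewhat different question.** It estimates the 24-week course under missing at random; the SAP formula describes the period observed.

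These points limit the size and reach. They do not remove the mismatch: a value covering a shorter period is labelled and analysed as one to Week 24, and no listed sensitivity analysis of this endpoint handles early stopping differently. The no-imputation sentence in SAP 2.4.2 might be read as leaving early stoppers out, but the explicit End of Study example points the other way.

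**Conclusion.** The point holds as a modest, correctable fault in the SP1 FAS sensitivity analysis, with a minor exposure in SP1 PPS. With no true difference, a 10-point imbalance moves the FAS estimate by about 0.01 to 0.11 for stops at Week 12 or earlier, and by roughly 0.01 to 0.02 on the middle course for Week 16-20 stops with an End of Study visit. Against a margin of 0.6, a false difference large enough to overturn the result by itself is implausible. Masking is the better reason to act: truncation pulls a true difference towards zero, with or without unequal withdrawal, in the one key secondary analysis meant to test a completer-only result.

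The direction follows from the formula for any course that improves or holds steady. The sizes rest on assumed courses, correlation and withdrawal by arm and time, none of which the documents give.

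**What to change.** 1. For SP1 FAS, estimate the 0-24 week average difference, with its 90% and 95% CIs, as a contrast of the visit-by-treatment LS means at Weeks 2, 4, 12 and 24, with weights 2/24, 5/24, 10/24 and 6/24, from the DAS28-CRP MMRM in SAP 4.6.1.2.
2. State one rule for assigning an early End of Study visit to a model visit. SAP 2.1.2 assigns it to a nominal visit only if it falls inside that visit's window and the nominal visit is absent, and otherwise keeps it separate. SAP 4.1.4 maps it to a scheduled visit by study day without that condition.
3. Keep the per-patient ANCOVA for SP1 PPS, and say that an average that does not reach Week 24 is not entered as a 24-week value.
4. Reconcile the protocol summary (MMRM) with protocol 9.5.1.1 (ANCOVA).

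The cost is SAP wording, one contrast in a model already planned, and the programming of the End of Study rule. The contrast uses nominal rather than actual visit days and relies on missing at random; the SAP should say both.
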